10.3 Demographic and Baseline Characteristics

Summary statistics will be provided per treatment group for demographic (race, gender, age) and other initial subject characteristics (e.g., concomitant disorders, concomitant treatments) will be provided per treatment group and for the total group.

10.4 Analysis Populations

The following analysis populations will be defined for the study:

- (1) The intent-to-treat (ITT) population will include all randomized patients. Patients will be analyzed according to their assigned treatment arm. All efficacy analyses will be completed in the ITT population.
- (2) Per-Protocol (Treatment Compliant): This population is defined as any participant that began the initial 4-week treatment or control phase, completed both the pre and post assessments, and met a minimum compliance level of 50%. Participants that received incorrect intervention after randomization will be excluded from this population.
- (3) The safety population will include all patients who receive study treatment. Patients will be analyzed according to actual treatment received. All safety analyses will be completed in the safety population.

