10.2 Sample Size Justification and Power Calculation

We will enroll up to 2,000 participants to achieve a 50% enrollment rate and 36% retention rate.

We aim to successfully retain 36% of enrolled families and have 360 parents and their child with autism aged 3-12 years old complete all study procedures (180 Treatment, 180 Control).

We will close out the study after enrolling 360 participants with completed endpoints, estimated for 90% power and 2-sided significance of .05 to detect minimal differences in VABS-III Socialization Standard Score of 3.1 points, consistent with the results of a GuessWhat feasibility study previously reported by our lab.

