10.5 Stratification, Subgroup Analysis and Pooled Analysis

Following consent, those subjects meeting all entry criteria will be randomized in a 1:1 ratio. Random blocks of size 2 or 4 will be utilized.

[Efficacy Endpoint Analysis](#)

1. Objective

To compare the change in outcome measure scores between treatment and treatment as usual groups in a clinical trial.

2. Study Design

Participants: Treatment and Treatment as Usual groups

Outcome Measure: Continuous outcome measure scores measured at baseline and follow-up on VABS-3 Socialization Subscale and Parent Stress Scale.

3. Statistical Hypotheses

Null Hypothesis (H_0): There is no difference in the change in outcome measure scores between treatment and control groups.

Alternative Hypothesis (H_1): There is a significant difference in the change in outcome measure scores between treatment and control groups, whereby treatment participants scores demonstrate improvement.

4. Variables

Independent Variable: Group (Treatment vs. Control)

Dependent Variable: Change in outcome measure scores (Post-test score - Pre-test score)

5. Statistical Method

Primary Analysis: Independent samples t-tests will be used to compare the mean change in outcome measure scores between treatment and control groups.

6. Assumptions

Normality: The change in outcome measure scores in each group should be approximately normally distributed. If not, consider transformations or non-parametric tests.

Equal Variances: The variances of change scores in the treatment and control groups should be approximately equal. If violated (checked using Levene's test), use Welch's t-test or report results with caution.

7. Statistical Software

Analysis Tool: SPSS, R, or any other statistical software capable of performing independent samples t-tests.

Descriptive analyses

Descriptive statistics (proportions for categorical variables, means, medians, standard deviations, and interquartile ranges for continuous variables) will be reported for all key patient variables, including baseline and demographic characteristics, use of medications, compliance, and study completion status. Data that are missing on key patient characteristics and the outcome will be fully described, including any patterns of missingness (i.e., any relationships between missingness of a variable and patient characteristics).

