A CONSORT diagram displaying the number of patients screened, eligible, and consented along with reasons for ineligibility will be provided. Graphical tools such as histograms, boxplots, and scatterplots will be created to assess quality of data and to display patterns over time.

Safety Analysis

Treatment related adverse events for GuessWhat intervention will be presented. Any adverse events occurring during any phase of the study judged by clinical sites' Primary Investigator (PI) to be related to the intervention will be recorded and presented in a table listing. The Safety population (see [analysis population details](#)) will be used for this analysis that will include randomized participants. The severity of each event will be evaluated by the PI and presented with the recorded events. If there are frequently occurring treatment related adverse events,

a frequency table will be included, to rank events from most frequent to most rare. Subjects will be included in the actual treatment group received.

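### The primary analysis is labelled ITT, but as specified it can use only families with a week-4 score, and no method is given for the rest

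*Combined protocol and SAP*

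**What the plan says.** **Population.** Section 10.4 puts every randomized participant in the ITT set, analysed as assigned, and states: "All efficacy analyses will be completed in the ITT population". A requirement for outcome data appears only in the per-protocol definition, whose members must have "completed both the pre and post assessments, and met a minimum compliance level of 50" percent. ITT is therefore meant to be wider than the families with both scores.

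**Test.** Section 10.5 gives one efficacy method: "Independent samples t-tests will be used to compare the mean change in outcome measure scores between treatment and control groups". The outcome is "Dependent Variable: Change in outcome measure scores (Post-test score - Pre-test score"). The fallbacks are a transformation, a non-parametric test or Welch's t-test.

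**Missing outcomes.** Section 10.5 says: "Data that are missing on key patient characteristics and the outcome will be fully described, including any patterns of missingness". Study completion status is also to be summarized, and the synopsis and 9.2 list missing data as a descriptive item. Neither section 10 nor any other part of the document names imputation, a likelihood-based model, weighting or a sensitivity analysis.

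**Participant flow.** "A CONSORT diagram displaying the number of patients screened, eligible, and consented along with reasons for ineligibility will be provided". Numbers randomized and week-4 retention by arm are not mentioned.

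**Expected loss.** Section 10.2 says: "We will enroll up to 2,000 participants to achieve a 50% enrollment rate and 36% retention rate". The target is 360 families who "complete all study procedures (180 Treatment, 180 Control"), and the study closes on completed endpoints. The synopsis pairs 500 to 2,000 enrolled with 360 to 900 completed.

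**The concern.** A family without a week-4 score has no change score, so neither the t-test nor any listed fallback can include it unless something supplies the missing value. The plan supplies nothing. An analyst following 10.5 literally would compare the families who returned week-4 forms and, under 10.4, report that comparison as ITT.

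Such a comparison keeps the protection of randomization only if returning the form is unrelated, in a way that differs by arm, to how the child changed. That cannot be taken for granted here. The outcome is parent-reported, 4.1 says outcome assessors are not blinded, and the activity monitoring and app reminders in 7.2 and 8.1 are aimed at families using the app while controls wait. The plan contains no analysis that would show how far the result depends on this assumption.

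**Working it through.** **1. The plan's own figure.** The accrual chain reproduces: 2,000 × 0.50 = 1,000, and 1,000 × 0.36 = 360. The 180 per arm cannot be reproduced, because no SD of change is stated. Solving backwards from 3.1 points, 180 per arm, two-sided 0.05 and 90% power (noncentral t) gives a standardized difference of 0.3426, so SD = 3.1 / 0.3426 = 9.05. This is an assumption, not a figure from the documents.

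**2. Share without a complete endpoint.** The week-4 share among randomized families is not stated. Reading enrolled as randomized (an assumption), the plan's figures give:

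- 10%: 1 − 900/1,000 (synopsis maximum completed; 50% of 2,000)
- 28%: 1 − 360/500 (synopsis minimums)
- 55%: 1 − 900/2,000 (synopsis maximums)
- 64%: 1 − 0.36 (retention in 10.2)
- 82%: 1 − 360/2,000 (fewest completed, most enrolled)

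The 64% refers to all study procedures, which include week 12 in 8.1 and section 13. Section 6.4 pays for the 4-week measures separately. Week-4 loss could therefore be lower.

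**3. From completers to all randomized.** Let D be the completer difference, m_T and m_C the missing shares in each arm, and g_T and g_C how much less non-completers change than completers in each arm. Then

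all-randomized difference = D − (m_T × g_T − m_C × g_C).

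If loss is equal in both arms (an assumption), this is D − m × gap, with gap = g_T − g_C. If loss differs by arm, even equal gaps shift the result, by g × (m_T − m_C).

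**4. Illustration at 64%.** Take D = 3.1 and hold the standard error at its completer value.

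- SE = 9.05 × √(2/180) = 0.954
- Significance threshold = 1.96 × 0.954 = 1.87 points
- Gap at which significance is lost = (3.1 − 1.87) / 0.64 = 1.92 points
- Gap at which the difference reaches zero = 3.1 / 0.64 = 4.84 points

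**5. Range.** The same formulas for each reading, with SE = 9.05 × √(2/450) = 0.603 and threshold 1.18 where 450 per arm complete:

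| Missing | Completers per arm | Gap to lose significance | Gap to zero |
|---|---|---|---|
| 10% | 450 | 19.2 | 31.0 |
| 28% | 180 | 4.4 | 11.1 |
| 55% | 450 | 3.5 | 5.6 |
| 64% | 180 | 1.9 | 4.8 |
| 82% | 180 | 1.5 | 3.8 |

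The rows differ in sample size as well as in loss, so they are separate readings of the plan and not a trend in missingness. The SD matters too. At 64% and 180 per arm, an SD of 8 gives (3.1 − 1.96 × 0.843) / 0.64 = 2.3 points, and an SD of 10 gives (3.1 − 1.96 × 1.054) / 0.64 = 1.6 points.

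**The case against.** The best defence is that this is an unspecified step and not an impossibility. Nowhere do the documents say that families without week-4 scores are dropped, and a t-test can be run on imputed change scores. That is correct. It remains true that no method for supplying those scores is written down, and that the only route the plan spells out leads to the observed scores alone.

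The plan is also open about attrition. The synopsis and 10.2 count completers, 10.2 ties the 90% power to completed endpoints, and 10.5 promises to describe missingness and completion. A reader might infer that loss is being concealed; the documents do not support that. Description, however, is not an estimator and does not test the assumption.

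The shares in the working are of enrolled families. Section 8.1 has families consented and enrolled at week 0 and randomized at app download in week 1, so some loss may come before randomization and would not be an ITT loss. This stands: 64% should not be read as the expected week-4 missing share among randomized families.

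Finally, a reader might infer from 7.2 that families marked lost to follow-up after reminders about inactivity are no longer asked for outcomes. The text does not say so, and 8.1 asks both arms for the week-4 measures without an activity condition. The gap is only that nothing says inactive families are still pursued.

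**Conclusion.** The concern holds. Sections 10.4 and 10.5 do not fit together: the stated population is everyone randomized, while the stated test, without a missing-data method, reaches only families with both scores. Because this governs the primary result, it must be fixed before analysis.

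The practical size depends on a week-4 missing share that the plan does not give; its own figures leave room for anything from 10% to 82%. On the 64% reading, a gap of about 1.9 points is enough to remove significance from a 3.1-point completer difference. That illustration assumes that enrolled means randomized, that loss is equal by arm, that the SD of change is 9.05, and that the standard error stays at its completer value.

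It is tempting to conclude that the trial will overstate the benefit of the app. The documents do not support that. A larger gap in controls would push the other way, and neither the size nor the direction of any bias can be derived.

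**What to change.** - **(a) Label.** In 10.4 and 10.5, call the t-test on observed change an analysis of participants with week-4 data.
- **(b) All-randomized analysis.** Pre-specify one under a stated missing-data assumption. An example is baseline-adjusted multiple imputation by arm, using baseline data, app use (9.2) in the treatment arm, and later assessments where obtained. Imputing by arm matters because controls may have started the app by those later assessments. Add a control-based or delta (tipping-point) sensitivity analysis. Whether the imputed analysis is primary or supportive is the sponsor's choice.
- **(c) Flow.** Extend the CONSORT diagram to the number randomized and week-4 retention by arm.
- **(d) Follow-up.** State that week-4 measures are sought from every randomized family in both arms, with the same reminders, regardless of app activity.
- **(e) Planning figures.** In 10.2, give the expected week-4 return rate among randomized families and reconcile the retention figures with the synopsis.

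**Cost.** Wording changes, week-4 requests to inactive families, and more analysis work. The imputed analysis relies on missing-at-random. App use helps only to the extent that it explains how returning and non-returning families differ, which is why the sensitivity analysis is needed. The resulting estimate may be smaller or less precise than the completer comparison.

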10.5 Stratification, Subgroup Analysis and Pooled Analysis

Following consent, those subjects meeting all entry criteria will be randomized in a 1:1 ratio. Random blocks of size 2 or 4 will be utilized.

[Efficacy Endpoint Analysis](#)

1. Objective

To compare the change in outcome measure scores between treatment and treatment as usual groups in a clinical trial.

2. Study Design

Participants: Treatment and Treatment as Usual groups

Outcome Measure: Continuous outcome measure scores measured at baseline and follow-up on VABS-3 Socialization Subscale and Parent Stress Scale.

3. Statistical Hypotheses

Null Hypothesis (H_0): There is no difference in the change in outcome measure scores between treatment and control groups.

Alternative Hypothesis (H_1): There is a significant difference in the change in outcome measure scores between treatment and control groups, whereby treatment participants scores demonstrate improvement.

4. Variables

Independent Variable: Group (Treatment vs. Control)

Dependent Variable: Change in outcome measure scores (Post-test score - Pre-test score)

5. Statistical Method

Primary Analysis: Independent samples t-tests will be used to compare the mean change in outcome measure scores between treatment and control groups.

6. Assumptions

Normality: The change in outcome measure scores in each group should be approximately normally distributed. If not, consider transformations or non-parametric tests.

Equal Variances: The variances of change scores in the treatment and control groups should be approximately equal. If violated (checked using Levene's test), use Welch's t-test or report results with caution.

7. Statistical Software

Analysis Tool: SPSS, R, or any other statistical software capable of performing independent samples t-tests.

Descriptive analyses

Descriptive statistics (proportions for categorical variables, means, medians, standard deviations, and interquartile ranges for continuous variables) will be reported for all key patient variables, including baseline and demographic characteristics, use of medications, compliance, and study completion status. Data that are missing on key patient characteristics and the outcome will be fully described, including any patterns of missingness (i.e., any relationships between missingness of a variable and patient characteristics).

A CONSORT diagram displaying the number of patients screened, eligible, and consented along with reasons for ineligibility will be provided. Graphical tools such as histograms, boxplots, and scatterplots will be created to assess quality of data and to display patterns over time.

Safety Analysis

Treatment related adverse events for GuessWhat intervention will be presented. Any adverse events occurring during any phase of the study judged by clinical sites' Primary Investigator (PI) to be related to the intervention will be recorded and presented in a table listing. The Safety population (see [analysis population details](#)) will be used for this analysis that will include randomized participants. The severity of each event will be evaluated by the PI and presented with the recorded events. If there are frequently occurring treatment related adverse events,

a frequency table will be included, to rank events from most frequent to most rare. Subjects will be included in the actual treatment group received.

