1. SYNOPSIS

Title	A Lead-in Study Evaluating Efficacy of GuessWhat Mobile App Therapy for Children With Autism
Design	Randomized, Investigator-Blinded,
Objectives	Determine whether GuessWhat Dtx can improve socialization in children with ASD after 4 weeks of use.
Endpoints	Primary: Change from week 0 to week 4 in the Vineland Adaptive Behavior Scales-3 Socialization Subscale, Comprehensive Parent Report Secondary: Change from week 0 to week 4 in Parent Stress Scale, and Child Emotion Recognition Score Exploratory/Descriptive: Descriptive analysis of child/parent surveys, treatment regimen compliance, demographics, missing data, and any resulting treatment related AEs
Study Sites	Participants will recruited by Stanford via remote online recruitment.
Planned Enrollment	A minimum of 500 to a maximum of 2,000 participants will be enrolled to achieve a minimum of 360 to a maximum 900 completed participants (n=180 - 450 in each of 2 arms) evaluable
Study Population	Autistic children 3-12 years old.
Subject Entry Criteria	Inclusion Criteria (1) Parent who is at least 18 years old of child with autism. (2) Child with autism is between 3 and 12 years old at time of baseline data collection. Exclusion Criteria (1) Parent does not have an Android or iOS smartphone compatible with GuessWhat App. (2) The parent is unable to speak/read in available translations of the study app: English, Spanish, Brazilian Portuguese.
Randomization	Block randomization stratified by child sex.
Treatment Regimen (Standard dose)	App is used 3 times a week for 15 minutes for 4 weeks

Duration of Study Participation	8 weeks
Statistical Methods	Independent Samples T-Tests
Study Measurements: Efficacy, Safety	Efficacy: Change in Vineland Adaptive Behavior Scales-3 Socialization Subscale week 0 to week 4 Safety: Adverse event reporting

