8.1 Screening and Enrollment Steps

Week 0/Screening and Baseline Assessment

Participants will be screened, consented, and enrolled entirely online using electronic data capture. Parents/Guardians and coordinators will complete the following steps prior to enrollment via online forms:

- Screening questionnaire completed online
- Informed Consent administered and obtained online (waiver of documentation approved)
- Baseline questionnaires completed (Demographics, Mobile Autism Risk Assessment (MARA), Parent Stress Scale, VABS-3 Socialization subscale parent report, Emotion Recognition Child online Task
- review of baseline data completed by coordinator

Week 1: Enrollment and Allocation

- Upon receiving notification with download link and download access code, participant downloads the app and is automatically randomized to treatment or control using a pre-defined block randomization scheme developed by the statistician.

[Weeks 1-4: Intervention](#)

If randomized to Control, participants will continue treatment as usual. When they log-in to the app, they will receive a message that they will wait a few more weeks before beginning treatment.

If randomized to Treatment, participants will be asked to play the app 3 times a week for 10-15 minutes for the next 4 weeks and they will receive weekly push notifications and email reminders.

[Week 4 Post-Test 1](#)

Treatment and Control will be asked to complete all outcome measures and will be asked about any changes in treatment or safety events at week 4. Participants will also be asked to complete a question assessing time spent playing with their child over the last month in emotion-centric theatrical play.

[Week 8 Post-test 2](#)

At week 4 from initial app download date, participants will be asked via email to complete all outcome measures as well as check-in on any changes in treatment and any safety events. These will be collected via RedCap online surveys.

[Week 12 Post-test 3 Follow-Up](#)

Treatment and Control will be asked to complete all outcome measures and will be asked about any changes in treatment or safety events at week 4. Participants will also be asked to complete a question assessing time spent playing with their child over the last month in emotion-centric theatrical play.

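### The primary t-test on change scores leaves precision unused: fitting baseline score (and child sex, if it is a stratum) would narrow the interval at no cost in data

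*Combined protocol and SAP*

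**What the plan says.** Section 10.5 (Efficacy Endpoint Analysis) sets the method: "Primary Analysis: Independent samples t-tests will be used to compare the mean change in outcome measure scores between treatment and control groups". Its list of variables has one predictor, "Independent Variable: Group (Treatment vs. Control", and defines the response as "Dependent Variable: Change in outcome measure scores (Post-test score - Pre-test score". The synopsis entry for statistical methods is simply "Independent Samples T-Tests". No baseline-adjusted model appears anywhere, even as a sensitivity analysis.

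If the change scores are not approximately normal, 10.5 says: "If not, consider transformations or non-parametric tests". If variances differ on Levene's test, it offers Welch's test or cautious reporting.

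On randomization, the synopsis says "Block randomization stratified by child sex". Section 10.5, although headed as covering stratification, gives the 1:1 ratio and then "Random blocks of size 2 or 4 will be utilized". Section 8.1 says participants are "automatically randomized to treatment or control using a pre-defined block randomization scheme developed by the statistician". Neither of these two sections names a stratum.

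Section 8.1 and the schedule in section 13 both place the VABS-3 Socialization report at week 0, before randomization.

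**The concern.** Taking post minus pre uses the baseline with its slope fixed at 1. Analysis of covariance (ANCOVA) estimates that slope. Under 1:1 allocation ANCOVA is, in large samples, never less precise than the change score, and it is more precise whenever the true slope differs from 1. The baseline is already needed to compute the change score, so nothing new has to be collected.

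Three things are at stake.

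- **Precision.** Completers are the scarce resource. Section 10.2 expects 2,000 × 0.50 × 0.36 = 360, or about 5.6 people at the start for each completer. A more efficient analysis gives a narrower interval, or some margin if 360 is missed.
- **Chance imbalance.** Given a baseline gap between the analysed arms, the change-score estimate is shifted by about −(1 − r) times that gap. ANCOVA removes this shift.
- **Discretion.** The normality fallback has no criterion, names no test and does not say which result counts. The primary p-value could therefore be settled after the data are seen.

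If sex is a stratum, omitting it makes the t-test conservative where sex predicts change, and does no harm where it does not.

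**Working it through.** **Inputs from the documents.** 180 completers per arm, a difference of 3.1 standard-score points, 90% power and two-sided alpha 0.05 (10.2, 10.1); 1:1 allocation (10.5). **Assumed, because the documents give no value:** r = 0.9, 0.8, 0.7 or 0.5, and the ratio k of the week-4 SD to the baseline SD.

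**1. The plan's own figure.** No SD is stated, so 180 per arm cannot be reproduced independently; the SD it implies can be solved for. Normal approximation: 3.1 × √(180/2) / (1.960 + 1.282) = 9.07. With the t distribution: 9.05. At that SD, the t-test's 95% CI half-width is 1.88 points.

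**2. Gain with equal SDs (k = 1).** Variance of the change score is proportional to 2(1 − r) and that of ANCOVA to 1 − r². The ratio is (1 − r²)/(2(1 − r)) = (1 + r)/2. Extra completers needed by the t-test = 2/(1 + r) − 1. ANCOVA residual SD = 9.05 × √((1 + r)/2), with 356 degrees of freedom at 180 per arm.

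| r | Variance ratio | Extra completers for t-test | ANCOVA power at 180/arm | N per arm for 90% | 95% CI half-width |
|---|---|---|---|---|---|
| 0.9 | 0.95 | 5% | 91.4% | 172 | 1.83 |
| 0.8 | 0.90 | 11% | 92.7% | 163 | 1.78 |
| 0.7 | 0.85 | 18% | 94.0% | 154 | 1.73 |
| 0.5 | 0.75 | 33% | 96.3% | 136 | 1.62 |

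Between r = 0.9 and r = 0.5 the saving is 2 × (180 − 172) = 16 to 2 × (180 − 136) = 88 completers.

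**3. Unequal SDs.** The variance ratio becomes k²(1 − r²)/(k² + 1 − 2rk). Extra completers needed by the t-test:

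| k | r = 0.9 | r = 0.8 | r = 0.7 | r = 0.5 |
|---|---|---|---|---|
| 1.2 | 2.3% | 0.3% | 3.5% | 14.8% |
| 0.8 | 64% | 56% | 59% | 75% |

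**4. Shift from a chance baseline gap (k = 1).** Holding the SD of change at 9.05 implies a cross-sectional SD of 9.05/√(2(1 − r)) = 20.2, 14.3, 11.7 and 9.05 for r = 0.9, 0.8, 0.7 and 0.5. One standard error of the baseline gap is that SD × √(2/180). Multiplied by (1 − r), the shift is 0.21, 0.30, 0.37 and 0.48 points, or 7% to 15% of 3.1.

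**5. Simulation check (4,000 runs per setting, bivariate normal).** Welch's t-test on change: mean estimate 3.10 to 3.12 for a true 3.1, type I error 4.8% to 5.3%, power 89% to 90%. ANCOVA with sex and HC3 standard errors: type I error 4.5% to 5.9%, power 90.8%, 92.6%, 94.9% and 96.4% for r = 0.9, 0.8, 0.7 and 0.5. Both methods are valid, and the gain matches the formula.

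**6. Normality fallback (8,000 null runs, 180 per arm).** If the smaller of the t-test and Mann-Whitney p-values may be taken, type I error is 5.7% for normal data and 7.2% for both heavy-tailed (t, 3 df) and skewed data. A fixed rule triggered by the Shapiro-Wilk test holds it at 4.9% to 5.2%.

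**The case against.** The strongest reply is that the planned test is pre-specified, valid and unbiased, that baseline is already used by subtraction, and that the gain cannot be sized from the documents. The power figures start from an SD solved backwards from the stated power. Holding it fixed while r varies also changes the implied population: the largest gain, at r = 0.5, goes with the smallest cross-sectional SD (9.05), and the smallest, at r = 0.9, with the largest (20.2). All of this stands. It limits how firmly the size can be stated, but not the direction, and the price is two of 358 degrees of freedom.

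A second reply is that the unstated SD matters more. If the pilot result in section 3.2 (5.27 points, p = 0.002, 72 children) is assumed to come from a paired t-test, the SD of change is 5.27 × √72 / 3.21 = 13.9. Power at 180 per arm is then about 56% unadjusted and 58% to 68% adjusted. That is a fair and separate problem, which adjustment would ease but not solve.

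Third, the fallback applies only when normality fails. With a strict Shapiro-Wilk trigger, type I error for normal data is about 5.0% even if the smaller p-value is then taken. This lowers the normal-data figure only. The plan sets no such trigger, and the heavy-tailed and skewed figures remain as a worst case of selective choice.

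Finally, silence about sex in 8.1 and 10.5 is not a contradiction of the synopsis. That is correct, but the analysis model cannot be settled until these sections agree.

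**Conclusion.** The concern holds as an improvement in precision. It is neither a validity failure nor, on the plan's own assumptions, a shortfall from 90% power. With equal SDs and r between 0.9 and 0.5, the change-score t-test needs 5% to 33% more completers than ANCOVA. If the week-4 SD is 1.2 times the baseline SD the figure is 0.3% to 15%; if it is 0.8 times, 56% to 75%. The correlation and the SDs are assumptions throughout, and all point values are on the standard-score scale used in 10.2.

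The open normality fallback could add up to about two percentage points of type I error under deliberate selection. Baseline adjustment corrects only the part of any dropout imbalance that the observed baseline score explains. The missing outcomes expected at 36% retention are a separate matter.

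**What to change.** In 10.5 and the synopsis, make the primary analysis one pre-specified linear model of the week-4 VABS-3 Socialization score on arm, baseline score and child sex, with heteroscedasticity-robust standard errors. Report the adjusted mean difference with its 95% CI. Using change as the response with baseline as a covariate gives the same arm coefficient, so the endpoint can still be described as change.

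- First reconcile the synopsis with 8.1 and 10.5 on whether sex is a stratum.
- Use the same model for the Parent Stress Scale and the Emotion Recognition score.
- Remove the open normality fallback and the Levene switch. Keep Welch's t-test on change as a named sensitivity analysis.
- State how a missing baseline score is handled, since 7.2 only flags incomplete baseline data.
- In 10.2, state the assumed SD of change and the correlation.

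The cost is protocol and SAP wording only: no new data, visits or participants.
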